
Our lab group has assessed the age of diagnosis and age of appropriate intervention in children with hearing loss in Kentucky. We have identified a statistically significant delay in diagnosis and treatment for patients from the Appalachian region of Kentucky. We are also examining the causative factors behind this delay. The lack of education and family support is a common theme in families that fail to follow-up or are delayed in their follow-up. We are proposing a study to examine the effect of a patient navigator to influence patient satisfaction, patient/family behavior and the age of diagnosis of pediatric hearing loss

2. Objectives:

Hypothesis: The assistance of a patient navigator for families with a newborn who failed a newborn hearing-screening test will result in improved patient compliance, patient satisfaction, and age of diagnosis and intervention of pediatric hearing loss.

Specific Aim 1: Examine the effect of a patient navigator to influence the age of diagnosis and intervention for pediatric hearing loss.

Specific Aim 2: Examine the effect of a patient navigator to influence patient satisfaction, knowledge, and compliance with the hearing evaluation and intervention process following newborn hearing screening.

Form B: Medical IRB Research Description

3. Study Design:

For Specific Aim 1, mothers of newborns failing birth hearing screening will be recruited. Participants will be placed into Appalachian and non-Appalachian stratum and then randomized into a patient navigator group or the standard of care group. The navigator group will receive an intervention consisting of educational support from a patient navigator. We will compare the non-adherence rates to obtain the recommended testing within 3 months between groups and strata. The timing of testing will also be assessed and compared between regional strata. At enrollment, we will collect data on maternal socioeconomic status, educational level, and distance from testing center and infant health. Findings will be correlated with adherence to follow-up and timing of services. If the child receives follow up before 3 months and it is determined that child has hearing loss he or she will be approached by a research staff member to participate in the second part of the study (Aim 2) to be randomized and either followed for one year by the patient navigator or to follow standard of care practice.

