Specific Aim 1: The same outcomes will be measured in both groups. Group 1 will be contacted every 2 weeks after discharge from the hospital regarding their child who failed the newborn hearing screen by the patient navigator. This contact will primarily occur through phone calls, but can also occur through email or text messages on a password protected phone if the patient prefers one of these communication methods. Communications between the patient and patient navigator will consist of inquiring on the health and development of the child, addressing questions about hearing, hearing loss, upcoming tests, and intervention services. The navigator will attempt to have these questions answered by clinical staff involved in the patients care and will communicate this to the family. Group 2 will not have navigator contact but will work directly with their hearing healthcare clinic and other referral centers for diagnostic and intervention services (THIS IS THE CURRENT STANDARD OF PRACTICE). Parents in each group of the children born at UKMC, children born at outside facilities (and referred to UKMC Audiology clinic for follow up testing), and children referred to CSHCN for follow up testing will be given a standard brochure that contains basic information about newborn hearing screening and a contact number regarding obtaining further assistance with the diagnostic testing and/or treatment. This is document produced and circulated by the state of Kentucky childhood early hearing detection and intervention agency (SEE APPENDIX 1). At the time of enrollment, parents of the child with the failed hearing screening will fill out a questionnaire which assesses patient satisfaction, knowledge, attitudes, and behaviors, along with some demographic information (**see attached**) from both groups. The subjects who are discharged from outside facilities will have the questionnaire completed by mail, email (through REDCap), or phone with the research staff member. Notes from phone conversations from navigator phone calls will be recorded by the navigator and then recorded on an excel spreadsheet. The data from the questionnaire and the other time points will also be recorded on an excel spreadsheet. At the follow up appointment the research team will also collect data on the outcome of the diagnostic testing. If subjects do not receive their diagnostic follow up within the 3 month time frame

Form B: Medical IRB Research Description

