a member of the research team will contact them by phone in order to complete the exit questionnaire and determine if they had diagnostic follow-up at another facility. If the patient cannot be reached by phone the UK research team will work collaboratively with CSHCN to find out (through the EHDI system) if these patients received follow up care in another clinic outside of the study or if they were lost to follow up. This data will be kept in a password-protected file on a password-protected computer and along with the consents will be kept in the locked office of the PI. This data will be kept for a total of 6 years after the conclusion of the study.

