Specific Aim 2: The same outcomes will be measured in both groups, but this Aim will focus on the timing of intervention from the hearing screening as an outpatient. The patients randomized to the navigator group will be contacted weekly-biweekly to provide educational and psychosocial support of participants with the same four conversation points from Aim 1. The testing that diagnosed hearing loss will be recorded into the EHDI database. At the time of enrollment, parents of the child with the failed hearing test will also fill out a questionnaire which assesses patient satisfaction, knowledge, attitudes, and behaviors, along with some demographic information (**see attached**) from both groups (navigator and non-navigator). We will have the patients complete the questionnaire at enrollment and 12 months after enrollment. We will also record the age of initial diagnostic test at their hearing healthcare clinic (depending on where the patient received diagnostic testing), age of definitive diagnosis of hearing loss, age of early intervention consultation, age of hearing aid fitting, and (if patient meets criteria for cochlear implantation) age of cochlear implantation. Parent(s) of children in this Aim will also receive another questionnaire, similar to the one they receive at the beginning of Aim 2 that assesses patient satisfaction, knowledge, attitudes and behaviors with follow up demographic information during the one year follow up. Notes from phone conversations from navigator phone calls and data from the questionnaire and at the other time points will be recorded by the navigator and then recorded on an excel spreadsheet. This data also will be kept in a password-protected file on a password-protected computer and along with the consents will be kept in the locked office of the PI. This data also will be kept for a total of 6 years after the conclusion of the study.

7. Resources:

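### In Aim 2 the navigator, who delivers the intervention and so knows allocation, is the named recorder of the questionnaire data on satisfaction and knowledge; Aim 1 names the navigator for call notes only.

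*Combined protocol and SAP*

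**What the plan says.** Section 2 (Objectives) states the aim: "Specific Aim 2: Examine the effect of a patient navigator to influence patient satisfaction, knowledge, and compliance" with hearing evaluation and intervention. Section 3 (Study Design) gives group 1 a navigator from diagnosis of hearing loss through the first year of life; group 2 has none.

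Section 6 (Research Procedures), Specific Aim 2, says that the same outcomes are measured in both groups and that the aim focuses on when intervention happens. Parents fill out a questionnaire on satisfaction, knowledge, attitudes and behaviors at enrollment and at 12 months. A further, similar questionnaire is mentioned for the one-year follow-up. Five ages are also collected, under the wording "We will also record the age of initial diagnostic test", and the list goes on to definitive diagnosis and then "age of early intervention consultation, age of hearing aid fitting, and (if patient meets criteria for cochlear implantation) age of cochlear implantation". The closing sentence on data handling covers call notes and adds that "data from the questionnaire and at the other time points will be recorded by the navigator and then recorded on an excel spreadsheet".

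Section 6, Specific Aim 1, is written differently. On call notes it says: "Notes from phone conversations from navigator phone calls will be recorded by the navigator and then recorded on an excel spreadsheet". The next sentence names no recorder: "The data from the questionnaire and the other time points will also be recorded on an excel spreadsheet". For the test result, "At the follow up appointment the research team will also collect data on the outcome of the diagnostic testing". For families not tested within 3 months, "a member of the research team will contact them by phone in order to complete the exit questionnaire".

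**The concern.** Satisfaction and knowledge are reported by parents, and parents cannot be blinded to whether they have a navigator. The handling of their answers can still be kept apart from the person being evaluated. The Aim 2 sentence does the reverse: it puts the data for these outcomes in the navigator's hands.

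The risk arises wherever recording leaves room for discretion: an answer given by phone, an unclear mark, a missing item, or a decision on whether to chase a late form. If such cases are handled differently in the two arms, the comparison of satisfaction or knowledge is distorted. The navigator contacts group 1 families weekly to biweekly in Aim 2, while no contact schedule is given for group 2, so the opportunity to complete or clarify answers may also differ by arm.

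**Working it through.** There is no planned figure to reproduce. The check sets the sections side by side and then counts the data concerned.

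**1. Does the recorder know allocation?** This is not stated in words but follows from section 3. Group 1 has navigator contact and group 2 does not, so the navigator's own caseload shows the arm.

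**2. What is the navigator named to record?**

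| Item | Aim 1 (section 6) | Aim 2 (section 6) |
|---|---|---|
| Call notes | Navigator | Navigator |
| Questionnaire data | No recorder named | Navigator |
| Data at other time points | No recorder named | Navigator |
| Diagnostic test outcome | Research team | Diagnosing test entered in the EHDI database; no role named |
| Exit questionnaire, families not tested by 3 months | Research team member | No counterpart |
| Five event ages | Not listed | Recorder given only as *we* |

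The Aim 2 sentence reads like the two Aim 1 sentences run together, which brings the questionnaire under the navigator. The text available gives no reason for the difference.

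**3. Which outcomes are affected?** Section 2 names three for Aim 2. The questionnaire supplies satisfaction and knowledge. Compliance is the third, and nothing shows that it depends on the questionnaire.

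**4. Can the sentence be carried out without a problem?** There are two cases.
- If the navigator records both arms, the recorder is unblinded and has a stake in one of them.
- If the navigator records group 1 only, data handling differs by arm, although the section intends the same outcomes in both.

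**5. How much data?** Inputs: expected Aim 2 enrollment from section 4, and questionnaire occasions and ages from section 6. No dropout is assumed.
- Subjects: 31 + 31 = 62.
- Questionnaires at enrollment and 12 months: 62 × 2 = 124.
- If the questionnaire during the one-year follow-up is separate from the 12-month one: 62 × 3 = 186.
- Only if the event ages are also covered: at most 62 × 5 = 310 dates, or 62 × 4 = 248 without cochlear implantation, which applies only to children who meet criteria.

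These counts give the volume of data handled. They do not measure bias.

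**The case against.** The strongest reply is that the sentence may describe clerical work. Parents fill out the questionnaire, and recording followed by entry in a spreadsheet can mean copying. Harm would require answers taken by phone or unclear on paper, and a navigator who resolves them differently by arm; the documents state neither. This stands, and it limits the point to a risk. It does not dispose of it, because the return route for Aim 2 questionnaires is not given. Mail, email through REDCap, and phone are described only for Aim 1 enrollment questionnaires from outside facilities.

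A reader might infer that the navigator also records the five event ages. The documents do not establish this. The ages are introduced with no recorder named, and the phrase about other time points could mean later questionnaire occasions. Aim 1 uses nearly the same phrase with no list of ages before it. The ages are also dated events, less open to judgement than ratings, and the diagnosing test goes into the EHDI database. No independent source is stated for the intervention ages, so the wording needs clarifying, but the criticism cannot rest on it.

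The contrast with Aim 1 should not be overstated either. Leaving the recorder unnamed does not show independent recording, and the research team's exit questionnaire is described only for families not tested within 3 months. A drafting slip in Aim 2 is as plausible as a deliberate choice. Either way, the sentence as written assigns the task and should be corrected.

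Finally, nothing available says that other research staff are blinded. Section 4 has research staff approach families who continue navigation from Aim 1, so staff may know the arm. This also stands: reassigning the task removes the provider's stake in the result, not knowledge of allocation.

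**Conclusion.** The point holds for the questionnaire data. The plan explicitly assigns their recording to the person who delivers the intervention and knows allocation, and two of Aim 2's three stated outcomes depend on them. The volume is 124 questionnaires, or 186 if a third is intended, assuming 62 subjects and no dropout.

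The documents do not support a claim that the results would be biased or would favor the navigator arm; neither size nor direction can be determined. They also do not support saying that the navigator elicits or judges answers, or that all of Aim 2 rests on the questionnaire. The navigator's role as an advocate for families (section 7) is not evidence of recording bias. Part of the text after section 8 was not available, so a safeguard there cannot be excluded.

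This is a change that should be made because the risk is avoidable and cheap to reduce. Confidence is medium, because the extent of the navigator's handling is not described.

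**What to change.** Amend section 6, Specific Aim 2, to say that:
- in both arms, questionnaires are self-completed, or taken and entered by existing research staff other than the navigator, using the same method and schedule;
- the navigator records call notes only;
- the phrase about other time points has a stated meaning. If it includes the event ages, the same non-navigator staff record them from the same type of source in both arms.

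State also whether the questionnaire during the one-year follow-up is the 12-month one or a third.

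The cost is a wording change and modest entry work for existing staff: about 124 questionnaires, or 186. If REDCap return is used, its described scope must be extended to Aim 2. If the ages are included, up to 310 dates are added, and some clinic records may have to be requested, since the documents do not show that EHDI holds every date. Sample size, arms and care do not change. Parents, and possibly staff, remain unblinded, so the risk is reduced but not removed.

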Patients and families that are involved may contact the navigator, PI and/or their primary care and/or referring physician if they experience any concerns with the research or if they would like to withdraw their participation from the study. Additionally, they may contact ORI Research Compliance Officer's toll-free [contact]) as a subject's primary contact point.

19. Research Involving Non-English Speaking Subjects or Subjects from a Foreign Culture: N/A**20. HIV/AIDS Research:** N/A**21. PI-Sponsored FDA-Regulated Research:** N/A
